#### 4.10.1 Adverse events

Adverse events (AEs) will be presented by MedDRA System Organ Class (SOC) and Primary Term (PT). Coding of verbatim terms will be performed by Ergomed and all relevant codes are stored in the database and it will be approved by the Sponsor before database lock (cf. DMP).

Only treatment-emergent adverse events (TEAE) will be analysed, i.e. all new and worsened pre-existing adverse events occurring on or after the initiation of IMP. It is assumed that for each change in intensity, relationship, or seriousness of an AE a new entry of the AE was recorded in the data capture database; hence such cases will be analysed like different phases of the same AE.

An overall summary of TEAEs will be presented including both the number and percentage of patients with a given AE category and the number of events:

- All TEAEs
- Serious TEAEs (STEAEs)
- Treatment-related TEAEs
- Treatment-related Serious TEAEs
- Severe TEAEs
- TEAEs leading to study drug discontinuation
- Fatal TEAEs

A descriptive analysis will be performed. Global incidences of primary system organ classes (SOC) and preferred terms (PT) will be calculated for:

- All TEAEs irrespective of the causality assessment
- Serious TEAEs (STEAEs)
- TEAEs by relationship
- STEAEs related to study drug
- TEAEs by maximum severity
- TEAEs leading to discontinuation
- Fatal TEAEs

Statistical Analysis Plan	Version 1.0		Page 26 of 37
Sponsor	SOM Biotech	Protocol No	SOMCT03

These tables will be presented by treatment group and also include summary lines for all SOCs and the occurrence of any event of the specified type. SOC terms will be presented according to the Internationally Agreed Sorting Order (MedDRA).

Multiple counts within a PT or SOC (repeated or different included terms or changes in descriptors) will be counted only once for the calculation of incidences. In addition to the incidences, the number of reported AEs (within a PT or SOC) will be included in the summaries.

Detailed listings of all fatal and other serious events will be provided (for section 14.3.2). All adverse events (i.e. TEAEs as well as non-treatment emergent events) will be listed in section 16.2.

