- Patients allocated to 400 mg/day treatment arm will receive 200 mg once daily (OD) the first week, and then 200 mg BID the second and third week.
- Patients allocated to 600 mg/day treatment arm will receive 200 mg OD the first week, 200 mg
   BID the second week, and then 300 mg BID the third week.
- Patients allocated to the placebo arm will take matching placebo capsules according to the same pattern, once a day during the first week and twice per day from the second week.

**Maintenance dose (from Visit 2 to Visit 5)**: the dose reached in each arm (200 mg BID or 300 mg BID or placebo) will be maintained for 7 additional weeks. At the end of this maintenance dose period, two evaluations will be performed one week apart, at Visit 4 (end of Week 9) and at Visit 5 (end of Week 10), to assess the treatment effect versus baseline.

End of study with 1-week down-titration and 1-week placebo washout (from Visit 5 to Visit 6): during the last 2 weeks (Week 11 and Week 12), the patients will be instructed to take only 1 capsule in the morning. The two arms receiving the active drug will be dispensed capsules dosed at 200 mg for one week to decrease the dosing to 200 mg/day. During the last week, all the patients will receive capsules of placebo.

Patients will return for a last visit (Visit 6) to assess the withdrawal of the drug.

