#### 4.3. RATIONALE FOR STUDY DESIGN

This 12-week Phase 2b study is designed to evaluate in parallel groups the efficacy, safety and tolerability of two doses of SOM3355 (400 mg/day or 600 mg/day, taken either as 200 mg or 300 mg BID) compared with placebo in HD patients with chorea. A previous Phase 2a study (SOMCT02) has already tested the effect of 400 mg/day SOM3355 (given as 200 mg BID) compared with placebo in a crossover design on 6-week periods, and it has shown a reduction of choreic symptoms measured by a significant decrease of the TMC score, and a good tolerability at the tested dose. For this Phase 2b trial, the regulatory authorities recommended a dose-finding study testing different fixed doses in parallel compared with placebo, to correctly assess the dose effect and determine the best dose to be tested in Phase 3.

It is deemed prudent to initiate the treatment by escalating the dose with weekly increases (200 mg OD the first week and 200 mg BID the second week to reach 300 mg BID on the third week for the patients allocated to the 600 mg/day treatment arm) for better tolerability and to reduce the risk of hypotension or bradycardia at the start of treatment. Then, the reached dose (400 mg/day or 600 mg/day) will be maintained for 7 additional weeks.

At the end of the maintenance dose, the study drug is down-titrated for one week (at 200 mg/day) to avoid an abrupt interruption of the dose, followed by a 1-week placebo washout period to assess the effect of the interruption of the study drug.

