## Adverse events:

All AEs summaries will be restricted to Treatment Emergent Adverse Events (TEAEs), which are defined as any AEs that occurs or worsens at or after the initiation of IMP. The AEs will be coded using the Medical Dictionary for Regulatory Activities (MedDRA) and tabulated by system organ class (SOC) and preferred term. Each AE summary will be displayed by treatment group.

Number of AEs, frequency and percentage of patients will be reported. For intensity level, the patient will be classified for the highest severity if the patients experienced several AEs.

Onset time of AE from initiation of IMP and AE duration will also be summarized.

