## 4.10 Safety

The Safety Analysis Set (SAF) will be used for the analysis of safety data. SAF includes all patients who were administered at least one dose of any study drug. Patients who are randomized and assigned a treatment but withdrew prior to dosing are not included in the safety population. Patients are included in the treatment group based on the treatment actually received.

Safety endpoints include:

- Incidence, frequency, and severity of AEs in each treatment group.
- Values and change from baseline in:
  - Vital signs: blood pressure (BP) (including orthostatic measurement), and heart rate (HR), weight.
  - o ECGs parameters (separately analysed by Banook/Phinc Development)
  - o Clinical laboratory test results (chemistry, hematology)
  - Physical examination findings,
  - Concomitant medications
  - C-SSRS assessing suicidality
  - o BDI scale assessing depression and suicidality (item #9)
  - o ESS assessing sleepiness
  - o TFC of the UHDRS® assessing functioning

Statistical Analysis Plan	Version 1.0		Page 25 of 37
Sponsor	SOM Biotech	Protocol No	SOMCT03

- FA of the UHDRS® assessing disabilities
- BARS assessing akathisia
- MoCA scale to assess cognitive disturbances
- o PBA-s to assess behavioural symptoms in HD.

Tolerability and safety data will be listed by patient (CSR section 16.2) and summarized descriptively by treatment group. Also, differences to Baseline will be presented whenever appropriate.

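### SAP 4.10.1 omits, without declaring it, the AE onset-time and duration summary in Protocol 9.4.3, so no AE summary it describes separates the titration, assigned-dose and interruption phases

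*SAP*

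**What the plan says.** **SAP 4.10.1 (Adverse events).** "Only treatment-emergent adverse events (TEAE) will be analysed, i.e. all new and worsened pre-existing adverse events occurring on or after the initiation of IMP". An overall summary and a set of SOC/PT incidence tables follow, covering among others all TEAEs, TEAEs by relationship and TEAEs leading to discontinuation. On layout: "These tables will be presented by treatment group". The section gives no end to the window, no split by dosing phase, and no summary of onset time or duration. All AEs are to be listed by patient.

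**Protocol 9.4.3 (Safety Analysis, adverse events).** The definition of TEAEs is just as open: "which are defined as any AEs that occurs or worsens at or after the initiation of IMP". The layout is also the same: "Each AE summary will be displayed by treatment group". It then adds: "Onset time of AE from initiation of IMP and AE duration will also be summarized".

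**SAP 2.2** records one departure from the protocol's statistical section, the multiplicity adjustment for CGI-C.

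**Grouping for safety (SAP 4.10).** "Patients are included in the treatment group based on the treatment actually received".

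**Dosing (Protocol 4.1).** Both active arms take 200 mg once daily in Week 1 and 200 mg BID in Week 2. They differ in Weeks 3-10 (200 mg BID against 300 mg BID). Both take 200 mg once daily in Week 11. For Week 12: "During the last week, all the patients will receive capsules of placebo".

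**Exposure (SAP 4.4)** is summarised separately for W1, W2, W3, W4-W10, W11 and W12.

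**The concern.** Protocol 4.3 presents the trial as a dose-finding study meant to inform the Phase 3 dose, and tolerability is part of that choice. It explains the stepwise start as being "for better tolerability and to reduce the risk of hypotension or bradycardia at the start of treatment", and it says the placebo week is there to assess the effect of stopping the drug. A reader of the AE tables will therefore want to know whether an event, or a discontinuation because of one, arose before the two active arms diverged, at the assigned dose, or after the dose was cut.

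The AE tables in SAP 4.10.1 do not answer that. The onset-time summary in Protocol 9.4.3 would have gone part of the way, and it is absent with no entry in SAP 2.2. The SAP's only planned look at patients who down-titrated correctly or incorrectly (SAP 3.6) describes TMC, not adverse events.

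**Working it through.** **1. Texts side by side**

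| Element | Protocol 9.4.3 | SAP 4.10.1 |
|---|---|---|
| TEAE window | From first IMP, no end | From first IMP, no end |
| Table layout | By treatment group | By treatment group |
| Onset time | Summarised | Not mentioned |
| Duration | Summarised | Not mentioned |
| Declared in SAP 2.2 | n/a | No |

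The pooling comes from the protocol. The SAP's own change is the loss of the last two summaries.

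**2. Treatment duration**

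Up-titration 3 + maintenance 7 + down-titration 1 + placebo 1 = 12 weeks = 84 days, of which 11 weeks are on active drug. This matches the protocol synopsis (11 weeks active, 1 week placebo).

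**3. Planned days by phase**

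| Phase | 400 mg/day arm | 600 mg/day arm | Days |
|---|---|---|---|
| W1 | 200 mg/day | 200 mg/day | 7 |
| W2 | 400 mg/day | 400 mg/day | 7 |
| W3-W10 | 400 mg/day | 600 mg/day | 56 |
| W11 | 200 mg/day | 200 mg/day | 7 |
| W12 | placebo | placebo | 7 |

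- Active arms treated alike: 7 + 7 + 7 + 7 = 28; 28/84 = 33.3%.
- 600 mg/day arm away from its labelled dose: 14 days at 200 mg/day + 7 at 400 mg/day + 7 on placebo = 28; 28/84 = 33.3%.
- 400 mg/day arm away from its labelled dose: 14 + 7 = 21; 21/84 = 25.0%.
- Interruption phase (W11-W12): 14/84 = 16.7% in each active arm.

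**4. Effect of pooling against placebo (rates assumed)**

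*Dilution.* Assume the event rate off the labelled dose equals the placebo-arm rate and the rate ratio on the labelled dose is R. The pooled ratio in the 600 mg/day column is (56R + 28)/84. For R = 1.5, 2 and 3 it is 1.33, 1.67 and 2.33.

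*Misattribution.* Assume no excess until W11-W12, then R times background. The pooled ratio is (70 + 14R)/84. For R = 2, 3 and 5 it is 1.17, 1.33 and 1.67, with no excess at the full dose.

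So pooling can push the figure in either direction.

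**5. 600 against 400 mg/day (weekly risks assumed)**

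Take 1.5% at 400 and 3.0% at 600 mg/day in W3-W10, and 1.5% in W11 and 0.45% in W12 for both arms. The W1-W2 risk, equal in both arms, varies. Incidence = 1 − product of (1 − weekly risk).

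W3-W10 alone: 1 − 0.985^8 = 11.4%; 1 − 0.97^8 = 21.6%. Ratio 1.90, difference 10.2 points.

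| W1-W2 weekly risk | 400 arm, 12 weeks | 600 arm, 12 weeks | Ratio | Difference (points) |
|---|---|---|---|---|
| 1.5% | 15.7% | 25.4% | 1.62 | 9.7 |
| 3.0% | 18.2% | 27.7% | 1.52 | 9.5 |
| 4.5% | 20.8% | 29.9% | 1.44 | 9.1 |

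Differences are taken from the rounded incidences. The ratio falls because near-identical events are added to both arms. The absolute excess shrinks by at most 10.2 − 9.1 = 1.1 points, and 0.011 × 43 is about half a patient per arm.

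**The case against.** The case for the plan is substantial, and most of it stands.

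- **Pooling over the whole regimen is legitimate.** Titration and tapering are part of what is being compared, and the protocol plans the same layout. This stands: the by-arm table is not an error.
- **Other safety data are already resolved in time.** On the planned schedule V2-V5 fall at the assigned dose and V6 follows the placebo week. Vital signs are summarised by group and time point (SAP 4.10.2), BDI and ESS are summarised by visit, and ECG has its own SAP. This stands for measured parameters. It does not cover reported events or discontinuations.
- **The complete output list is a separate document (SAP Appendix 1).** It may contain the missing summaries. The omission is therefore shown for the SAP text only.

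A reader might also infer stronger conclusions that the documents do not support:

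- *That events are counted under the randomised dose.* Safety grouping is by treatment actually received. For a patient dosed as assigned, the pooling is the same either way.
- *That interruption events cannot be separated.* By-patient listings are planned, Protocol 7.4.2.1 puts onset, last dose before the event and duration in them, and exposure is reported by period. Separation is possible by hand; what is missing is a planned summary.
- *That the dose relation is hidden.* In the illustration above the risk difference barely moves.
- *That bradycardia and hypotension will cluster in Weeks 1-2.* Protocol 4.3 gives a reason for escalating slowly. It does not forecast when events will occur, and the first on-treatment visit is Day 21.
- *That dose comparisons should rest on W3-W10.* That would condition on remaining in the study and set aside early intolerance.

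**Conclusion.** The point holds as a gap in planned reporting. Two parts need no assumptions. First, SAP 4.10.1 leaves out a summary that Protocol 9.4.3 specifies, and SAP 2.2 does not say so. Second, no AE summary described in the SAP distinguishes the three dosing phases, although the active arms are treated alike on 28 of 84 planned days (33.3%) and 14 of 84 (16.7%) belong to the interruption phase.

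The practical effect on the 600 versus 400 mg/day comparison depends on event rates that the documents do not give. With the assumed risks it is visible on the ratio scale (1.90 against 1.44-1.62) and small on the difference scale (10.2 against 9.1-9.7 points). Against placebo, pooling could dilute or inflate an apparent effect.

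The by-arm table remains the main safety comparison. The primary efficacy analysis is not affected. The correction is worth making because this is a dose-finding trial with an explicit interruption phase.

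**What to change.** In SAP 4.10.1:

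1. Restore the AE onset-time and duration summary from Protocol 9.4.3. If it is deliberately dropped, declare and justify that in SAP 2.2.
2. Keep the overall by-arm tables as the main comparison.
3. Add supplementary tables by phase at onset (W1-W2, W3-W10, W11-W12) for TEAEs, treatment-related TEAEs and TEAEs leading to discontinuation. Use patients at risk or exposure in each phase as denominator, regrouping the SAP 4.4 periods. Label these tables descriptive.
4. State when the TEAE window closes.
5. State how events are assigned to phases when the onset date is partial. SAP 4.1.2 sets a first-dosing-month onset with unknown day to the first dosing day, which would move a possible Week 3 or 4 event into W1-W2.
6. State the assignment rule for patients who down-titrate incorrectly (SAP 3.6). SAP 4.4 treats intake dates within visits as theoretical, so the W11/W12 boundary needs this.

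**Cost.** A few more tables and some SAP wording, using data already collected. Counts per phase will be smaller. Later phases include only patients who remain in the study, so they cannot support a formal dose comparison. No dosing or clinical rule changes.

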## 4.10.2 Vital signs

The following vital signs parameters will be assessed at each of the visits (from Visit 0 to Visit 6) as per schedule of assessment (except height only at Visit 0).

- Systolic blood pressure (SBP)
- Diastolic blood pressure (DBP)
- Heart rate
- Body weight

Four sequential measures of Blood Pressure should be performed as follows: sitting position for at least 5 minutes, supine position at least 5 minutes, standing position for 1 minute and 3 minutes. Orthostatic BP is calculated as change from supine to standing position after 1 and 3 minutes.

The following summaries will be provided:

- A summary of the observed absolute values and change from baseline in each vital sign parameter by treatment group and time point separately for sitting, supine, 1 min standing and 3 min standing
- A time profiles of the mean values for each vital sign parameter by treatment group separately for sitting, supine, 1 min standing and 3 min standing with SEM

A summary of the incidence of drop in SBP of  $\geq 20$  mmHg or drop in DBP of  $\geq 10$ mm Hg will be presented, where drop in BP is calculated as orthostatic BP.

#### 4.10.3 ECG

All ECGs will be performed after at least 5 minutes' rest in a supine or semi-supine position. To assess safety 12-lead ECGs will be recorded at Screening visit (Visit 0), inclusion visit (Visit 1), Visit 2, Visit 3 (in some countries Spain, UK & Germany), Visit 4, and Visit 6. At the inclusion, the ECG will be triplicated i.e., 3 successive records at 5 minutes of intervals and the average of all parameters will be calculated for baseline reference. All ECG are tele transmitted to a central reading centre (Banook) and analyzed within 48 hours by a cardiologist.

Statistical Analysis Plan	Version 1.0		Page 27 of 37
Sponsor	SOM Biotech	Protocol No	SOMCT03

ECG analysis is described in a separate Statistical Analysis Plan and results will be reported separately.

## 4.10.4 Laboratory variables

The following laboratory measurements will be taken at the Visit 0 (screening visit), at Visit 3 (interim visit at the end of Week 6), and at Visit 5 (end of maintenance dose at end of Week 10).

Hematology		
Red blood cell count	Mean corpuscular hemoglobin	Reticulocytes
Hematocrit	Mean corpuscular volume	White blood cell count with differ-
Hemoglobin	Platelet count	ential (neutrophils, lymphocytes, monocytes, eosinophils, basophils)
Clinical chemistry		
Alanine aminotransferase	Aspartate aminotransferase	Alkaline phosphatase
Albumin	C-reactive protein	Calcium
Total Protein	Creatine kinase (CPK)	Phosphate
Bicarbonate	Creatinine	Chloride
Bilirubin, direct and total	Urea	Potassium
Gamma glutamyl transpeptidase	Glucose	Sodium
Other		
Pregnancy test in women of child	bearing potential	

## Continuous laboratory data:

- Continuous data laboratory safety data (original values and change from baseline) will be summarized using descriptive statistics per visit and treatment group.
- Frequencies of high and low values with respect to the normal range will be displayed by visit and treatment group
- Shift tables comparing each post-baseline visit with baseline with respect to normal range will be displayed by treatment group
- In addition, abnormal values outside reference ranges (with assessment by investigator, NCS/CS) will be summarized in a listing per visit and per patient.

Vertical boxplot of laboratory values per parameter and per visit with outliers will be presented.

The lab values may be transformed to common units before analysis and summaries and analyses will only be performed on values converted to common units. However, original values and units can be found in laboratory listings. If repeated determinations at the same

Statistical Analysis Plan	Version 1.0		Page 28 of 37
Sponsor	SOM Biotech	Protocol No	SOMCT03

sampling times were performed (e.g., due to sample clotting) the values of the latest sample will be used in the analysis. However, all measurements will be included in laboratory listings.

The incidence of abnormal values out of ranges will be summarized for laboratory tests using descriptive statistics. These summaries will include all post baseline values (including scheduled, unscheduled, and early termination visits). Listing with outliers greater or lower than upper normal range will be presented.

## 4.10.5 Physical examination

Physical examination will be performed at each visit. Results of physical examination will be listed by patient and summarised in a frequency table displaying the absolute and relative frequency for normal/abnormal findings for each body system by treatment group and visit.

#### 4.10.6 Concomitant Medications

Concomitant medications, including medications that are taken on an as needed basis and occasional therapies, will be monitored during the study. All concomitant medications will be coded using the WHO drug Global thesaurus.

The incidence of concomitant medications will be summarized using descriptive statistics by WHO Drug Global Preferred Term (INN). Patients are counted only once in each PT category. In addition to the incidences, the number of reported CMs (within PT) will be included in the summaries. Concomitant medications will include all medications taken from the first day of study drug administration up to the end of study as defined in the study protocol.

#### 4.10.7 C-SSRS assessing suicidality

The C-SSRS is a questionnaire performed by trained study personnel that should be done at baseline and at each visit during the study to assess the status of the patient regarding suicide ideation and the risk of suicide attempt. The "Baseline/Screening" C-SSRS form provided at Screening collects the history of suicide attempts, while for subsequent visits the C-SSRS form termed "Since the Last Visit" should be used.

C-SSRS will be assessed at each visit.

The Columbia-Suicide Severity Rating Scale Screening/Baseline Version (C-SSRS-BL) is assessed at Visit 0 and Visit 1. The Columbia-Suicide Severity Rating Scale Since Last Visit (C-SSRS-SLV) is assessed at each visit after randomisation (Visit 2, Visit 3, Visit 4, Visit 5 and Visit 6).

Frequency counts and percentages of the C-SSRS outcomes: Suicidal Behavior or Suicidal Ideation at Baseline, Suicidal Behavior or Suicidal Ideation Post Dosing, and shifts from baseline will be summarized as categorical data using descriptive statistics.

Statistical Analysis Plan	Version 1.0		Page 29 of 37
Sponsor	SOM Biotech	Protocol No	SOMCT03

## 4.10.8 BDI scale assessing depression

BDI is 21-question multiple-choice self-report inventory. The questionnaire is composed of items relating to symptoms of depression such as hopelessness and irritability, cognitions such as guilt or feelings of being punished, as well as physical symptoms such as fatigue, weight loss, and lack of interest in sex.

Each item has four possible degree of severity rated from 0 to 3, and the patient is asked to choose the one that is closest to how he/she feels. The 21 items are summed linearly to create a score which ranges from 0 to 63. It can be administered as an interview by the clinician or as a self-report instrument.

## The item #9 assessing suicidality includes the following:

- 0. "I don't have any thoughts of killing myself."
- 1. "I have thoughts of killing myself, but I would not carry them out."
- 2. "I would like to kill myself."
- 3. "I would kill myself if I had the chance."

